##### 7.5.4.1.3 Eliciting and recording adverse event information

The investigator is to record all directly observed AE, and all AEs spontaneously reported by the parent/patient, in the CRF using concise medical terminology.

When possible and appropriate, a diagnosis rather than individual signs and symptoms shall be recorded. The investigator is responsible for obtaining sufficient information to determine seriousness, causality and outcome of each AE.

#### **Severity assessment**

For the purpose of consistency, the investigator will use the grading provided in Table 12 to describe the maximum intensity of the AE. The grading is based on the NCI CTCAE (version 4.03).

**Table 12**                      **Severity grade definitions according to NCI CTCAE (version 4.03)**

Grade I	Mild; asymptomatic or mild symptoms; clinical or diagnostic observations only; intervention not indicated
Grade II	Moderate; minimal, local or non-invasive intervention indicated; limiting age-appropriate instrumental Activities of Daily Living (ADL)

Grade III	Severe or medically significant but not immediately life-threatening; hospitalization or prolongation of hospitalization indicated; disabling; limiting self-care ADL
Grade IV	Life-threatening consequences; urgent intervention indicated

Note the distinction between the seriousness (serious/non-serious) and the intensity (severity) of an AE. **Severe** is a measure of intensity; thus, a **severe** reaction is not necessarily a **serious** reaction. For example, a headache may be severe in intensity, but would not be classified as serious unless it met one of the criteria for serious events listed above.

### Causality assessment

For each AE, the investigator or sub-investigator must make a causality assessment on the basis of his/her clinical judgment to determine if there is a reasonable possibility that the IMP(s) caused the AE. The AE is assessed as related or not related to the IMP(s) with the following definitions:

#### Related

The AE follows a reasonable temporal sequence from the study product administration, and cannot be reasonably explained by the subject's clinical state or other factors (e.g., disease under study, concurrent diseases, or concomitant medications).

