### **7.4.2 Identity of investigational medicinal products**

SOBI003 is provided as concentrated solution for i.v. infusion, 20 mg/mL, in 5-mL injection vials. Each vial contains 4 mL. Ten vials are packed in one box/outer carton. Vial and outer carton labeling will comply with national regulatory requirements. To facilitate accurate drug accountability, vial-specific numbers are printed on the vial labels.

The drug substance is manufactured by [REDACTED]

[REDACTED]. The drug product is manufactured by [REDACTED]

3 days, then the investigator should discuss with the Sponsor's MD to determine the timing of the next infusion (i.e., whether to await the next scheduled infusion).

Within 30 to 60 minutes prior to each infusion, a single dose of a non-sedative antihistamine should be administered. The antihistamine can either be e.g., cetirizine, levo-cetirizine, loratadine, des-loratadine or fexofenadine, and the administered doses will be in compliance with locally approved labeling. The antihistamine agent is selected at the discretion of the investigator. Antipyretic medication may also be administered, at the discretion of the investigator.

The actual doses of SOBI003 to be administered should be based on the patient's body weight at 4-week intervals (i.e., the actual dose administered at Weeks 25 to 28 is based on the body weight obtained pre-infusion at Week 25, the actual dose administered at Weeks 29 to 32 is based on the body weight obtained pre-infusion at Week 29, etc.). The body weight is obtained either on the day prior to the infusion or the day of infusion. For a body weight < 25 kg, the targeted total infusion volume is 100 mL. For a body weight  $\geq$  25 kg, the targeted total infusion volume is 250 mL. If the infusion bag contains an overfill volume, the infusion should continue until the infusion bag is emptied.

The final concentration of SOBI003 in the infusion bag will be calculated based on the added volume of SOBI003 to the infusion bag, and the total volume in the infusion bag.

The SOBI003 infusions are initially given over a period of 4 hours. When no more dose increases are expected, and the intensified study assessments associated with dose adjustments are completed (Section 7.5.1.7), the infusion period in individual patients may step-wise be decreased at the discretion of the investigator. The minimal infusion period is 1 hour.

Infusion rate schedules are provided in a separate IMP manual.

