#### Not Related

The AE does not follow a reasonable temporal sequence from study product administration, or can be reasonably explained by the subject's clinical state or other factors (e.g., disease under study, concurrent diseases, and concomitant medications).

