#### 7.5.4.1.5 Follow-up of unresolved adverse events

All AEs should be followed until they are resolved or the investigator assesses them as chronic or stable, or the patient's participation in the study ends, i.e., until Day 7 of Week 104 (End of Study). How to report changes in an ongoing AE during a patient's participation in the study is described in the CRF instructions.

In addition, all serious and non-serious AEs assessed by the investigator as related to SOBI003 should continue to be followed until they resolve or until the investigator assesses them as "chronic" or "stable", even after the patient's participation in the study is over.

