15.2.5 Adverse Events by Relationship to Study Drug

Treatment emergent AEs will be summarized by system organ class, preferred term and relationship to study drug (related, unrelated). The summarization will be performed for the total safety analysis set and for the pivotal sub group. The table will display the number and percentage of patients with at least one drug-related TEAE recorded at each level of summarization. The total number of events along with the number and percentage of patients with at least one drug-related treatment emergent AE will also be displayed.

Treatment emergent adverse events as judged by investigator as possible, probable or definite will be classed as related. Those recorded as not related or unlikely will be classed as unrelated. In the event of missing relationship information, the relationship will be imputed as related.

SAEs will be summarized in the same way.

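### The causality definitions record an event as Not Related whenever something else reasonably explains it, which is narrower than the protocol's own reasonable-possibility test, and the SAP maps a scale the protocol does not define

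*Protocol*

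**What the plan says.** Protocol section 7.5.4.1.3, under Causality assessment, sets the standard: the investigator uses clinical judgment to "determine if there is a reasonable possibility that the IMP(s) caused the AE". It then ties the answer to a two-way choice: "The AE is assessed as related or not related to the IMP(s) with the following definitions".

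- **Related** needs a reasonable temporal sequence and, in addition, that the event "cannot be reasonably explained by the subject's clinical state or other factors (e.g., disease under study, concurrent diseases, or concomitant medications".
- **Not Related** applies if the temporal sequence is lacking, "or can be reasonably explained by the subject's clinical state or other factors", with the same three examples of other factors.

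SAP section 15.2.5 describes the input differently. Events "as judged by investigator as possible, probable or definite will be classed as related"; those recorded as unlikely or not related are classed as unrelated; a missing assessment is imputed as related.

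The classification is then used in several places. Protocol section 9.4.7.1 tabulates AEs by relation to the product. SAP section 15.2 counts patients with related TEAEs, and section 15.2.5 summarises related TEAEs and SAEs. Protocol section 7.5.4.1.5 requires that "all serious and non-serious AEs assessed by the investigator as related to SOBI003 should continue to be followed until they resolve", or are judged chronic or stable, even after participation ends.

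**The concern.** A standard of reasonable possibility allows more than one candidate cause. The definitions do not: once another reasonable explanation exists, the drug is ruled out as a recorded cause. The investigator is asked one question and made to answer a stricter one.

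This matters in this trial because competing explanations are built into the population and the regimen. Patients have a progressive disease with behavioural, sleep and later motor and seizure manifestations (Protocol section 5.1.1). Co-medication accompanies every dose: "Within 30 to 60 minutes prior to each infusion, a single dose of a non-sedative antihistamine should be administered". Anaesthesia or sedation is planned at Weeks 52 and 104. The study has one arm and 9 to 12 patients, so no concurrent comparison can expose a skewed attribution.

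At stake is whether the related-event tables mean what the protocol's stated standard says they mean, and whether some events that meet that standard lose their mandatory post-study follow-up.

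**Working it through.** The documents give no figure on this point, so the check is logical. Take two conditions from the definitions: T, the timing is reasonable; A, there is a reasonable alternative explanation.

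- Related = T and not A.
- Not Related = not T, or A.

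By De Morgan's rule the second is the exact negation of the first, so there is no middle category and no overlap.

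| T | A | Recorded as | Can the reasonable-possibility test be met? |
|---|---|---|---|
| yes | no | Related | yes |
| yes | yes | Not Related | yes, when drug and alternative are both reasonable |
| no | no | Not Related | not ordinarily |
| no | yes | Not Related | not ordinarily |

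Only one of the four cells gives Related. The conflict is in the second row, where the opening standard can point to related while the definition requires Not Related.

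**Direction.** Assume that an event with reasonable timing and no other reasonable explanation meets the reasonable-possibility test. Then everything recorded as Related also meets the standard, and the only misclassified events are those in row two that meet it but are recorded as Not Related. The error against the protocol's own standard can therefore only run downward.

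**Size.** Let q be the share of events meeting the standard that also have another reasonable explanation. The related count then falls by the fraction q. Neither document gives event counts, causality splits or any other basis for q, so a percentage would only restate whatever was assumed.

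**Does the SAP correct it?** Compare the response scales.

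| Document | Values recorded | Classed as related | Classed as unrelated |
|---|---|---|---|
| Protocol 7.5.4.1.3 | related, not related | related | not related |
| SAP 15.2.5 | possible, probable, definite, unlikely, not related | possible, probable, definite | unlikely, not related |

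The SAP counts a merely possible event as related. Under the protocol, such an event with a second reasonable explanation has already been recorded as not related, and the SAP leaves that value as unrelated. The missing-data rule acts only on blank entries, so it does not bring the event back.

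**Reach.**

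- Affected: the related-TEAE and related-SAE summaries named above, and post-study follow-up under Protocol section 7.5.4.1.5 for events that did not lead to treatment withdrawal.
- Possibly affected: expedited reporting of serious, unexpected adverse reactions (Protocol section 7.5.4.1.4), so far as the term adverse reaction rests on the investigator's judgment.
- Not affected: the primary endpoint, which is all TEAEs and SAEs (Protocol section 6.1.1), and the investigator's duty to report SAEs, which applies regardless of causality (section 7.5.4.1.4).

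**The case against.** The best defence is that the definitions still leave room for judgment. The trigger is a reasonable explanation, not any conceivable one, and an investigator may find the disease an unconvincing explanation for a given event. That is true, and it limits how often the second row arises. It does not help once the alternative is judged reasonable, because the definition then leaves no choice.

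Several stronger readings are tempting, and the documents do not support them.

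- *The antihistamine is an alternative explanation for every event.* A reader might multiply 80 infusions by 9 to 12 patients and cite 720 to 960 premedicated infusions. That shows only that a co-medication is always present. Protocol section 5.2 gives pretreatment as a measure against hypersensitivity and infusion reactions, so it is not a natural explanation for the main expected drug risk.
- *Disease explanations are nearly always available.* Section 5.1.1 places seizures and motor decline in the final phase and fatal respiratory infections around the second to third decade. The comparison population is 12 to 72 months old at baseline. Behavioural and sleep symptoms fit that age better.
- *Only related events are followed after the study.* Section 7.3.3.1 follows events leading to treatment withdrawal whatever their cause, and section 7.5.4.1.2 collects SAEs to 28 days after the last dose unless a directly following sponsor extension collects them.
- *Events drop out of expedited reporting.* Every SAE goes to the contract research organization within 24 hours for medical assessment and on to the sponsor's drug safety department. The protocol does not tie expediting to the investigator's entry alone.
- *Little else separates drug from disease.* The plan has AE tables by dose level, AEs overlaid on exposure, and AEs by antibody status and titre (Protocol section 9.4.7.1, SAP sections 15.2.1 and 16.2). None of these needs a causality call. The data monitoring committee also reviews safety data.

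It can also be said that the SAP mapping is conservative and that the CRF instructions, which are not among the documents, may settle the scale. The mapping is conservative only for values it receives, and the CRF cannot be checked here.

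**Conclusion.** The point holds. The protocol states one causality standard and makes the investigator apply a narrower one, and the SAP assumes a response scale that the protocol does not define. Nothing elsewhere in either document resolves this. Followed as written, the rule lowers the related-event counts against the protocol's own standard. The direction rests on the assumption stated in the working; the size is unknown.

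The consequence is limited to descriptive relatedness summaries, post-study follow-up of events that did not cause treatment withdrawal, and possibly expedited reporting. A reader might infer that the trial's main safety result is biased. It is not, because the primary endpoint has no causality filter. The point should still be corrected, because the related-event tables will be read as applying the stated standard when they do not.

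**What to change.** Reword the two definitions in Protocol section 7.5.4.1.3 to match its opening standard.

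- *Related:* the timing relative to dosing is reasonable and there is a reasonable possibility that the product caused or contributed to the event, even if another factor may also have contributed.
- *Not Related:* there is no reasonable possibility that the product caused the event.

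Change SAP section 15.2.5 to the same two categories, keep the rule that missing counts as related, and check that the CRF and its completion guide collect exactly these values.

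The cost is wording in the protocol, CRF guide and SAP, with no new visits, samples or patients. The downside is real. With weekly infusions, most on-treatment events start within about seven days of a dose, so timing will seldom exclude the drug. More events will be classed as related, some of them disease-driven, and expedited reports may rise. Without a control arm that over-attribution also blurs the related-event table, so it should be read beside the all-event tables and the exposure and antibody displays already planned.

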#### Not Related

The AE does not follow a reasonable temporal sequence from study product administration, or can be reasonably explained by the subject's clinical state or other factors (e.g., disease under study, concurrent diseases, and concomitant medications).

#### 7.5.4.1.4 Serious adverse event reporting

Both serious and non-serious AEs are to be reported on the AE page of the CRF as specified in the CRF instructions. The form for collection of SAE information is not the same as the general AE CRF page. Where the same data are collected, the forms must be completed in a consistent manner. For example, the same AE term should be used on both forms.

Any SAE must be reported by the investigator if it occurs during the clinical study whether or not the SAE is considered to be related to the investigational product. An SAE report consists of the SAE form including medical history and concomitant medications. A copy of these forms must be emailed or faxed **within 24 hours** at:

- SAE reporting email address: [[contact]](mailto:[contact])
- SAE reporting toll [contact]
- SAE reporting country specific toll-free fax numbers

In addition, to the SAE reporting to INC, the investigator must via email notify the Sobi Medical Director and [[contact]](mailto:[contact]).

The investigator shall provide INC Research with sufficient information to enable a complete medical assessment of the reported event. Best efforts shall be made by the investigator to provide INC Research with additional information related to any SAE as requested.

The investigator should not wait to receive additional information to document fully the event before notification of a SAE, though additional information may be requested. Where applicable, information from relevant laboratory results, hospital case records, and autopsy reports should be obtained. All new information obtained, relevant to an SAE report, should be forwarded to INC Research within the same timeframe as the initial information.

Instances of death, congenital abnormality, or an event that is of such clinical concern as to influence the overall assessment of safety, if brought to the attention of the investigator at any time after cessation of study drug administration and linked by the investigator to this study, should be reported to the study monitor.

Sobi and/or INC Research will promptly notify all relevant investigators and the regulatory authorities of findings that could adversely affect the safety of subjects, impact on the conduct of the study or alter the independent ethics committee (IEC)/institutional review board (IRB) approval/favorable opinion of the study. In addition, INC Research, on behalf of Sobi, will expedite the reporting to all concerned investigators, to the IECs/IRBs, where required, and to the regulatory authorities of all adverse reactions that are both serious and unexpected. The expedited reporting to the regulatory authority in the U.S.A. will however be managed by Sobi.

#### 7.5.4.1.5 Follow-up of unresolved adverse events

All AEs should be followed until they are resolved or the investigator assesses them as chronic or stable, or the patient's participation in the study ends, i.e., until Day 7 of Week 104 (End of Study). How to report changes in an ongoing AE during a patient's participation in the study is described in the CRF instructions.

In addition, all serious and non-serious AEs assessed by the investigator as related to SOBI003 should continue to be followed until they resolve or until the investigator assesses them as "chronic" or "stable", even after the patient's participation in the study is over.

#### 7.5.4.2 Laboratory safety assessments

Biochemistry, hematology, coagulation and urine analyses are conducted at a central laboratory (BARC). The time points for sample collection are summarized in Table 13 as well as the analyses performed at each sampling occasion.

At the discretion of site personnel, urine collection bags will be used as needed.

In case of acute infusion reaction or anaphylactic reaction (taken at an AE grade III or greater but may also include grade II at the discretion of the investigator, central laboratory analyses): C-reactive protein (hsCRP), IL-1ra, TNF $\alpha$ , IgE, and tryptase.

Depending on the severity of the reaction and at the discretion of the investigator additional analyses may be performed at local laboratory to better understand the mechanism of the reaction.

Clinically significant laboratory values should be reported as AEs (see Section 7.5.4.1.1 for details).

Sampling details are provided separately in the Study laboratory manual.

**Table 13 Safety laboratory assessment time points**

Analyses	Study visit	Sampling time point(s)
Biochemistry (1.5 mL blood): Aspartate aminotransferase (AST), Alanine aminotransferase (ALT), Total bilirubin (if >upper limit of normal [ULN] then also direct and indirect bilirubin), Creatinine, Albumin, Potassium (K), Sodium (Na), Calcium (Ca), non-fasting Glucose, and C-reactive protein (CRP). Hematology (0.5 mL blood): Hemoglobin (Hb), Erythrocytes, White blood cell count (WBC), Differential blood count and Platelet count. Coagulation (1.7 mL): PT/INR, APTT, and Fibrinogen. Urinalysis (dip-stick analyses, central laboratory): pH, Glucose, Proteins, and Blood	Weeks 38, 52, 78 and 104	Pre-infusion (Day 1)
	In case of SOBI003 dose adjustment	For the first 3 infusions following dose adjustment: Pre-infusion (Day 1)
C-reactive protein (hsCRP), IL-1ra, TNF $\alpha$ , IgE, and tryptase (6.4 mL blood)	In case of infusion/anaphylactic reaction	

#### 7.5.4.3 Immunogenicity

Serum and CSF samples are collected for central laboratory analysis of SOBI003 ADAs by a validated immunoassay method (York Bioanalytical Solutions Limited, York, UK). Assays are being developed for assessment of neutralizing antibodies, both for antibodies inhibiting cellular uptake and for enzyme activity inhibiting antibodies (BioAgilytix, Hamburg, Germany). At each sampling occasion, a blood volume of 1.5 mL will be collected.

Serum samples are collected prior to start of SOBI003 infusion at Weeks 38, 52, 78 and 104, and during Early Termination. Triplicate aliquots are required for each sampling time point.

CSF samples (0.5 mL) are collected at Weeks 52 and 104.

If the dose of SOBI003 is adjusted in a patient, serum samples are collected prior to start of the first adjusted infusion and then prior to the 3rd adjusted infusion i.e., at 2 occasions per dose adjustment.

For patients with an ADA-positive serum sample, the following will also be determined in serum: ADA titer, IgG subclasses, and presence of NAb.

For patients with an ADA-positive CSF sample, the following will also be determined in CSF: ADA titer and presence of NAb.

Should any patient permanently discontinue SOBI003 treatment, then a serum sample will be collected 30 to 40 days after the last SOBI003 administration for ADA assessment. Should the sample be ADA-positive, then the ADA titer will be determined and ADA samplings will continue at approximately monthly basis until the ADA has disappeared or titers have stabilized at a lower level.

The impact of ADAs on the safety, tolerability, and PK of SOBI003 will be explored, as well as the potential impact on HS levels in CSF, serum and urine.

Sampling details are provided separately in the Study laboratory manual.

#### **7.5.4.4 Vital signs**

Vital signs (blood pressure, heart rate, body temperature, respiratory rate, and oxygen saturation) are measured at each SOBI003 infusion.

At Weeks 25 to 104, vital signs are measured pre-infusion, mid- infusion and within 1 hour after end of each infusion. Vital signs are also measured at Early Termination.

If the dose of SOBI003 is adjusted in a patient, vital signs are measured pre-infusion, 1, 2 and 3 hours after start of infusion, within 1 hour after end of infusion, within 6-7 hours after start of infusion, within 8-12 hours after start of infusion, 24 hours after start of infusion and 48 hours following infusion for the first 3 infusions. During these weeks, continuous pulse oximetry is assessed from pre-infusion until completion of SOBI003 infusion.

Blood pressure and heart rate are measured in accordance to each clinic's standard procedures. When the clinical situation allows, the assessments should preferably be done in supine position after the patient has rested comfortably for at least 5 minutes. Body temperature is measured in degrees Celsius using a tympanic thermometer according to each clinic's standard procedures. The pulse oximetry sensor device is placed on a fingertip or earlobe (according to standard routines at the study site). In case of need to prolong infusions (i.e., > 4 hours) at any time during the study, pulse oximetry monitoring will be applied, as judged by the investigator.

Clinically significant abnormal vital signs values should be reported as AEs (see Section 7.5.4.1.1 for details).

